12.0 Version History

Table 3. SAP Version History Summary

Version	Date	Summary
1.0	09 October 2018	Original version
2.0	02 November 2020	
Added Section 5.0, Section 6.0, Section 7.0, Section 10.0 and Section 11.0 following the new SAP template.
 
Section 3.2: added some secondary endpoints and 'other endpoint' to be consistent with the protocol amendment.
 
Section 3.4, Section 9.2, Appendix J: added 'other safety topics of interest' to include information of dupilumab related safety topics of interest.
 
Section 4.0: changed the definition of PP Population to be aligned with classification plan.
 
Section 5.0, Section 6.0: added information of 'before Week 16' to summarize the status before Week 16, which is the time for the primary endpoint.
 
Section 7.1: added IgE summary.
 
Section 7.3: Clarified that the concomitant medication will be summarized in Safety Population instead of ITT Population.
 
Section 8.2 through Section 8.5: Added details of efficacy analysis. Introduced NRI-C and NRI to incorporate the COVID-19 pandemic's affection to the study.
 
Section 8.6: Changed 'Baseline vIGA-AD (moderate [vIGA-AD 3], severe [vIGA-AD 4])' to 'Baseline vIGA-AD (moderate or milder [vIGA-AD \leq3], severe [vIGA-AD 4])' to incorporate those who entered study with vIGA-AD<3.
 
Section 9.2: Clarified the definition of TEAE in order to more accurately reflect the safety profile of the active drugs
 
Section 9.2 through Section 9.4: added details of safety analysis

13.0 References

Appendix A. Protocol Deviations

The number and percentage of subjects who reported at least one of the following protocol deviation categories will be provided.

- Subject entered into the study even though s/he did not satisfy entry criteria.
- Subject developed withdrawal criteria during the study and was not withdrawn.
- Subject received wrong treatment or incorrect dose of study.
- Subject took prohibited concomitant medication.
- Subject with deviation related to COVID-19 Pandemic

Appendix B. Definition of Adverse Events of Special Interest

AEs of Special Interest (AESI) will be identified by the following CMQ, SMQ, and other search criteria:

AESI	Type of MedDRA Query	Broad or Narrow Search	SMQ/CMQ Search Criteria
Serious Infections	CMQ		"Infections" – Subset for SAEs
Opportunistic Infection excluding tuberculosis and herpes zoster	CMQ		"Opportunistic Infection excluding tuberculosis and herpes zoster"
Possible Malignancy	SMQ	Narrow	"Malignancies"
Malignancy	SMQ		"Malignant Tumours"
Non-Melanoma Skin Cancer (NMSC)	SMQ/CMQ	SMQ Narrow	Skin Malignant tumours (Narrow SMQ) removing Melanoma CMQ
Malignancy excluding NMSC			Malignancy Narrow SMQ and removing NMSC output
Lymphoma	SMQ		"Malignant Lymphomas"
Hepatic Disorder	SMQ	Narrow	"Drug Related Hepatic Disorders"
Adjudicated Gastrointestinal Perforations	Medical review of events identified by the "Gastrointestinal Perforation" SMQ Narrow search		
Anemia	CMQ		"Non-Hemolytic and Non-Aplastic Anemias"
Neutropenia	CMQ		"Hematological Toxicity – Neutropenia"
Lymphopenia	CMQ		"Hematological Toxicity – Lymphopenia (Veliparib Product Specific)"
Herpes Zoster	CMQ		"Herpes Zoster"
Creatine Phosphokinase (CPK Elevation)	PT		Search only for the PT of "Blood creatine phosphokinase increased"

AESI	Type of MedDRA Query	Broad or Narrow Search	SMQ/CMQ Search Criteria
Renal Dysfunction	SMQ	Narrow	"Acute Renal Failure"
Active Tuberculosis	CMQ		"Active Tuberculosis"
Adjudicated cardiovascular events ^a	Output from CAC		
MACE*			
Cardiovascular Death			
Non-fatal Myocardial Infarction			
Non-fatal Stroke			
Other Adjudicated Cardiovascular Events			
Undetermined/Unknown Cause of Deaths			
Adjudicated Thrombotic Events	Output from CAC		
VTE**			
Deep Vein Thrombosis			
Pulmonary Embolism			
Other Venous Thrombosis			
Arterial Thromboembolic Events (non-cardiac, non-neurologic)			

CAC = Cardiovascular Adjudication Committee; CMQ = company MedDRA query; PT = preferred term;

SMQ = standard MedDRA query

a. Reviewed and adjudicated by an independent Cardiovascular Adjudication Committee in a blinded manner.

* MACE: Major Adverse Cardiovascular Events, defined as cardiovascular death, non-fatal myocardial infarction and non-fatal stroke.

** VTE: Venous thromboembolic events, defined as deep vein thrombosis (DVT) and pulmonary embolism (PE) (fatal and non-fatal).

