Primary results from the ongoing Phase 2 study demonstrated superior efficacy of upadacitinib with an acceptable safety profile at the selected doses for Phase 3 (15 mg and 30 mg once daily [QD]) compared to placebo in subjects with moderate to severe AD. Taken together, the efficacy and safety data from the Phase 2 AD study and cumulative safety data from ongoing Phase 2 and 3 programs in other disease indications support further development of upadacitinib in subjects with moderate to severe AD.

Adverse events such as infections, herpes zoster reactivation, malignancies, and hematologic AEs have been observed with JAK inhibition. Events of deep vein thrombosis and pulmonary embolism have been reported in patients receiving JAK inhibitors including upadacitinib. Malignancies have been reported in the RA clinical studies for upadacitinib. Based on the integrated data from the Phase 3 RA studies, there were comparable incidence rates of malignancies other than non-melanoma skin cancer (NMSC) between the upadacitinib 15 mg QD and 30 mg QD groups with long-term treatment. NMSC is a common malignancy in the general population. Although the incidence rate of NMSC was higher in the upadacitinib 30 mg group compared to the upadacitinib 15 mg group in the integrated analysis data, the risk of patients experiencing a NMSC when receiving upadacitinib 15 mg and 30 mg in the Phase 3 RA studies did not appear to increase over time. Based on review of the data available, no pattern of the types of malignancies was noted, the malignancies are expected for a population of patients with moderately to severely active RA, and the standardized incidence rate is within the expected range for the general population. The safety profile specific to upadacitinib is evolving, with safety results to date consistent with those known to be associated with JAK inhibition, with non-serious infections (e.g., upper respiratory tract infection or nasopharyngitis) being the most commonly reported AEs. In addition, laboratory changes observed with upadacitinib include elevations of serum transaminases, lipids, creatinine, and creatine phosphokinase; both increased and reduced hemoglobin, depending on Baseline inflammatory burden; and reductions in white blood cell counts, including natural killer (NK) cells.

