### Medical Complaints/Adverse Events and Serious Adverse Events

An AE is defined as any untoward medical occurrence in a subject or clinical investigation subject administered a pharmaceutical product and which does not necessarily have a causal relationship with this treatment. An AE can therefore be any unfavorable and unintended sign (including an abnormal laboratory finding), symptom, or disease temporally associated with the use of a medicinal (investigational) product, whether or not the event is considered causally related to the use of the product.

Such an event can result from use of the drug as stipulated in the protocol or labeling, as well as from accidental or intentional overdose, drug abuse, or drug withdrawal. Any worsening of a pre-existing condition or illness is considered an AE. Worsening in severity of a reported AE should be reported as a new AE. Laboratory abnormalities and changes in vital signs are considered to be AEs only if they result in discontinuation from the study drug, necessitate therapeutic medical intervention, meets protocol specific criteria (see Section 6.2 regarding toxicity management) and/or if the investigator considers them to be AEs.

The investigators will monitor each subject for clinical and laboratory evidence of adverse events on a routine basis throughout the study. All adverse events will be followed to a satisfactory conclusion.

If any of the following events are reported, then the following supplemental report must be completed:

Adverse Event	Supplemental Form
Cardiac events Myocardial infarction or unstable angina Heart failure Cerebral vascular accident and transient ischemic attack Venous thromboembolism	Cardiovascular (Cardiac) AE eCRF Myocardial Infarction and Unstable Angina AE eCRF Heart Failure Adverse Event eCRF Cerebral Vascular Accident and Transient Ischemic Attack AE eCRF Embolic and Thrombotic Event (Non-Cardiac, Non-central nervous system [CNS]) eCRF
Herpes Zoster Infection	Herpes Zoster AE eCRF
ALT/AST > 3 ULN	Hepatic Abnormal Laboratory Value Supplemental eCRF Hepatic Supplemental Local Labs eCRF (if applicable) Hepatic Supplemental Procedure eCRF (if applicable)
Serum creatinine > 1.5 × the baseline value and > ULN Serum creatinine ≥ 2.0 mg/dL	Renal Abnormal Laboratory Value Supplemental eCRF Renal Supplemental Local Labs eCRF (if applicable) Renal Supplemental Procedure eCRF (if applicable)

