### Adverse Events of Special Interest

The following AEs of special interest for upadacitinib will be monitored during the study:

- Serious infections
- Opportunistic infections
- Herpes zoster
- Active Tuberculosis
- Malignancy (all types)
- Adjudicated Gastrointestinal perforations
- Adjudicated cardiovascular events (e.g., major adverse cardiovascular event [MACE])
- Anemia
- Neutropenia
- Lymphopenia
- Increased serum creatinine and renal dysfunction
- Hepatic events and increased hepatic transaminases
- Elevated creatine phosphokinase (CPK)
- Adjudicated embolic and thrombotic events (non-cardiac, non-Central nervous system [CNS])

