Serum Creatinine	
 
• If serum creatinine is > 1.5 × the Baseline value and > ULN, repeat the test for serum creatinine (with subject in an euvoletic state) to confirm the results. If the results of the repeat testing still meet this criterion, then interrupt study drug and re-start study drug once serum creatinine returns to ≤ 1.5 × Baseline value and ≤ ULN.
 
 
For the above serum creatinine elevation scenario, complete the appropriate supplemental renal eCRF(s).

Laboratory Parameter	Toxicity Management Guideline
Creatine Phosphokinase	
 
• If confirmed CPK value <math>\geq 4 \times</math> ULN and there are no symptoms suggestive of myositis or rhabdomyolysis, the subjects may continue study drug at the investigator's discretion.
 
• If CPK <math>\geq 4 \times</math> ULN accompanied by symptoms suggestive of myositis or rhabdomyolysis, interrupt study drug and contact AbbVie TA MD.
 
 
For the above CPK elevation scenarios, complete supplemental increased CPK eCRF.

Ab = antibody; ALC = absolute lymphocyte counts; ALT = alanine aminotransferase; AST = aspartate aminotransferase; CPK = creatine phosphokinase; DNA = deoxyribonucleic acid; eCRF = electronic case report form; HB = hepatitis B; HBc Ab+ = Hepatitis B core antibody positive; HBs Ab = Hepatitis B surface antibody; HBV = hepatitis B virus; INR = international normalized ratio; PCR = polymerase chain reaction; TA MD = Therapeutic Area Medical Director; ULN = upper limit of normal

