Immunoglobulin E percent change from baseline will be provided by visit. A summary including number of subjects, min, 25% quartile, median, 75% quartile, and max will be provided by visit. No statistical modeling will be applied.

Potentially Clinically Important Laboratory Values

Laboratory abnormalities will be evaluated based on Potentially Clinically Important (PCI) criteria (NCI CTCAE criteria of Grade 3 or above) with a grade worsening compared to Baseline. For each laboratory PCI criterion, the number and percentage of

subjects who have a laboratory value meeting the criteria will be summarized. Listings will be provided to summarize subject-level laboratory data for subjects meeting PCI criteria. The PCI criteria are defined in [Appendix C](#) using CTCAE 4.03.

Liver Function Tests

According to FDA's Guidance for Industry "Drug-Induced Liver Injury: Premarketing clinical evaluation (July 2009), when aminotransferase (AT) abnormalities indicating hepatocellular injury are accompanied by evidence of impaired hepatic function (bilirubin elevation $> 2 \times$ ULN), in the absence of evidence of biliary obstruction (i.e., significant elevation of ALP) or some other explanation of the injury (e.g., viral hepatitis, alcohol hepatitis), the combined finding (i.e., Hy's Law cases) represents a signal of a potential for the drug to cause severe DILI. For the purpose of assessing for potential Hy's law cases, the frequencies and percentages of subjects with post-baseline liver specific function test values that meet the following criteria of potential clinical interest should be presented:

- ALT $\geq 3 \times$ ULN
- ALT $\geq 5 \times$ ULN
- ALT $\geq 10 \times$ ULN
- ALT $\geq 20 \times$ ULN
- AST $\geq 3 \times$ ULN
- AST $\geq 5 \times$ ULN
- AST $\geq 10 \times$ ULN
- AST $\geq 20 \times$ ULN
- TBL $\geq 2 \times$ ULN
- Alkaline phosphatase $\geq 1.5 \times$ ULN
- ALT and/or AST $\geq 3 \times$ ULN and concurrent TBL $\geq 1.5 \times$ ULN
- ALT and/or AST $\geq 3 \times$ ULN and concurrent TBL $\geq 2 \times$ ULN

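### SAP Appendix B gives no search term for the creatinine half of the protocol's renal AESI, and the PCI cut-off for creatinine leaves a band of interruption-level rises uncounted

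*SAP*

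**What the plan says.** **The AESI.** Protocol 6.1 (Adverse Events of Special Interest) lists "Increased serum creatinine and renal dysfunction" as a single item. SAP 9.2.2 summarises AESIs through MedDRA queries on adverse event terms and refers to Appendix B for the search criteria. The only renal row there is labelled renal dysfunction and uses the narrow query "Acute Renal Failure". No row names creatinine. In the same table, CPK elevation is found through one laboratory preferred term ("Search only for the PT of" raised blood CPK).

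**The laboratory count.** SAP 9.3 states: "Laboratory abnormalities will be evaluated based on Potentially Clinically Important (PCI) criteria (NCI CTCAE criteria of Grade 3 or above", with a grade worsening from Baseline also required. Table C-2 sets creatinine Grade 3 at above 3 and up to 6 × ULN, or above 3 × Baseline, and Grade 4 at above 6 × ULN.

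**The protocol's own creatinine criterion.** Table 3 acts when serum creatinine is above "1.5 × the Baseline value and > ULN, repeat the test for serum creatinine". It continues: "If the results of the repeat testing still meet this criterion, then interrupt study drug". Protocol 6.1 asks for a renal supplemental eCRF at the same level, and also at 2.0 mg/dL or more. Under Protocol 6.1 a laboratory abnormality is an adverse event if, among other routes, it "meets protocol specific criteria (see Section 6.2 regarding toxicity management").

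**The concern.** AESIs are a stated safety endpoint (Protocol 3.5, SAP 3.4), and the trial is a head-to-head comparison. Protocol 2.2 says that "laboratory changes observed with upadacitinib include elevations of serum transaminases, lipids, creatinine, and creatine phosphokinase". Its list of the most common dupilumab adverse events (injection site reaction, conjunctivitis, blepharitis) does not include creatinine. Creatinine is therefore a laboratory change on which the arms could plausibly differ, and the protocol put it in the AESI list by name.

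The SAP has two summaries in which a reader would look for it: the renal AESI line and the PCI table. The first names no creatinine term. The second starts well above the level at which the protocol acts. If the query does not contain raised-creatinine terms, a difference between arms at the level of drug interruption would not show in either summary and would have to be found among single preferred-term rows. SAP 1.0 says that changes from the protocol's analyses are outlined in Section 12.0. That section records no change to the renal AESI, so a reader cannot tell whether the creatinine part was dropped on purpose.

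**Working it through.** No statistical figure in the plan is at issue, so there is none to reproduce. The check has two parts.

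**1. Interruption criterion against PCI cut-off.** Let b be baseline creatinine in multiples of ULN. The baselines below are assumed, for illustration.

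- Interruption criterion (Protocol Table 3, both conditions, confirmed on repeat): I = max(1.5b, 1).
- Lowest PCI cut-off (SAP Table C-2, either condition): P = min(3b, 3).
- Band that meets the interruption criterion but is not PCI: from I to P, when P > I.

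| b (× ULN) | I (× ULN) | P (× ULN) | Width P − I |
|---|---|---|---|
| 0.33 | 1.00 | 1.00 | 0 |
| 0.50 | 1.00 | 1.50 | 0.50 |
| 0.67 | 1.00 | 2.00 | 1.00 |
| 0.80 | 1.20 | 2.40 | 1.20 |
| 1.00 | 1.50 | 3.00 | 1.50 |
| 1.20 | 1.80 | 3.00 | 1.20 |
| 1.50 | 2.25 | 3.00 | 0.75 |
| 2.00 | 3.00 | 3.00 | 0 |

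For b up to 2/3 the width is 3b − 1, which is positive once b exceeds 1/3. From 2/3 to 1 it is 3b − 1.5b = 1.5b. Above 1 it is 3 − 1.5b, which reaches zero at b = 2. The band therefore exists for every baseline between 1/3 and 2 × ULN and is widest at b = 1. Values above P are PCI-counted, provided the grade worsens.

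**2. Creatinine beside the other Table 3 laboratory parameters.**

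- Neutrophils, lymphocytes, leukocytes, platelets: the upper bound of PCI Grade 3 (1.0, 0.5, 2.0 and 50 × 10⁹/L) equals the Table 3 interruption level (1000, 500, 2000 and 50,000/µL).
- Hemoglobin: the absolute level matches (8 g/dL = 80 g/L). The other trigger, a fall of 3.0 g/dL or more, is not PCI, but anemia has its own AESI query.
- ALT/AST: the Appendix B label also omits the laboratory half of the protocol item, but SAP 9.3 adds counts from 3 × ULN, alone and with concurrent bilirubin.
- CPK: PCI starts above 5 × ULN and Table 3 acts from 4 × ULN, but CPK has its own preferred-term row.
- Creatinine: no search row of its own, and no laboratory count below Grade 3.

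Creatinine is thus the only laboratory component of the protocol's AESI list with neither a query of its own nor a threshold count below Grade 3.

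**Where a rise in the band would appear.** As an adverse event under Protocol 6.1 it should enter the treatment-emergent tables by system organ class and preferred term (SAP 9.2.1). By-visit summaries and CTCAE shift tables (SAP 9.3) cover selected parameters, and creatinine is not named among them. SAP 9.2.1 tabulates events leading to discontinuation, not to interruption.

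**The case against.** A reader might infer that creatinine rises which interrupt study drug appear in no AESI or PCI count. The documents do not support that. Rises above 3 × Baseline or 3 × ULN also meet the interruption criterion, and they are PCI-counted. The contents of the narrow query are in neither document, so whether it captures a creatinine event depends on those contents and on the term the investigator reports. A shortened row label does not prove that a component was dropped: the hepatic label is shortened in the same way. All of this stands and limits the point.

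It is also fair to say that Grade 3 and above is a uniform PCI rule, not meant to mirror Table 3, and that Protocol 7.4 promises only pre-defined criteria. No promise is broken by the PCI table, and the same kind of gap exists for CPK. The liver thresholds serve a stated purpose, screening for Hy's Law cases. Creatinine is a listed analyte with CTCAE grades in Table C-2, so it may well be among the selected shift-table parameters, and those tables would show grades below 3. The events are not lost, since the general adverse event tables remain.

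What the objection does not remove is the contrast within the SAP. Transaminases and CPK each have a second route into a dedicated summary; creatinine has none that is stated, although the protocol names it in the AESI.

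**Conclusion.** The point holds in two limited parts. First, the SAP states no search for the creatinine half of a protocol AESI, and whether the renal query covers it is left open. Second, the PCI table omits creatinine rises between max(1.5 × Baseline, ULN) and min(3 × Baseline, 3 × ULN). The second part follows from the two documents alone; only the illustrative baselines are assumed.

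Its size can be given as a threshold band but not as a number of subjects. The documents give no rate of creatinine events in either arm, so a reader who infers that the renal AESI line understates upadacitinib events by some number, or that it will show nothing in both arms, goes beyond them. No safety data are lost and no endpoint is invalidated. The change is still worth making, because it aligns a stated safety endpoint with its protocol definition at very little cost. Nothing here bears on which clinical threshold is right.

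**What to change.** **Appendix B.** Restore the protocol's label for the renal AESI and add a preferred-term search for raised blood creatinine alongside the existing query, in the form used for CPK. If the query already contains the term, this changes nothing.

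**SAP 9.3.** Name creatinine among the shift-table parameters. Next to the PCI counts, add by arm the number and percentage of subjects with creatinine above 1.5 × Baseline and above ULN. Show any occurrence and confirmed on repeat as separate lines, because Table 3 interrupts only on confirmation and a count without that step is not a count of interruption-level events. The protocol asks for the repeat as soon as possible but sets no window, so the SAP should say which later sample counts as confirming. Derive the count from laboratory values, not from completed renal eCRFs, since that form is also triggered at 2.0 mg/dL or more.

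**Cost.** One search row, one laboratory count shown on two lines, and a named shift-table parameter, all from data already collected. The renal AESI figure may look slightly less favourable. The Grade 3 PCI rule and every clinical threshold stay as they are.

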Appendix C. Potentially Clinically Important Criteria for Safety Endpoints

The criteria for Potentially Clinically Important (PCI) laboratory findings are described in Table C-1 and Table C-2, and the PCI criteria for vital sign findings are described in Table C-3.

Table C-1. Criteria for Potentially Clinically Important Hematology Values

Hematology Variables	Grade	Units	Definition of Potentially Clinically Important
			Very Low
Hemoglobin	3	g/L	< 80.0
Platelets count	3	10 ⁹ /L	25.0 - < 50.0
	4	10 ⁹ /L	< 25.0
Leukocytes	3	10 ⁹ /L	1.0 - < 2.0
	4	10 ⁹ /L	< 1.0
Neutrophils	3	10 ⁹ /L	0.5 - < 1.0
	4	10 ⁹ /L	< 0.5
Lymphocytes	3	10 ⁹ /L	0.2 - < 0.5
	4	10 ⁹ /L	< 0.2

Note: A post-baseline value must be more extreme than the Baseline value with at least one CTCAE grade of worsening to be considered a potentially clinically important finding.

Table C-2. Criteria for Potentially Clinically Important Chemistry Values

Chemistry Variables	Grade	Units	Definition of Potentially Clinically Important	
			Very Low	Very High
ALP	3	U/L		$> 5.0 \times \text{ULN} - 20.0 \times \text{ULN}$
	4	U/L		$> 20.0 \times \text{ULN}$
SGOT/AST	3	U/L		$> 5.0 \times \text{ULN} - 20.0 \times \text{ULN}$
	4	U/L		$> 20.0 \times \text{ULN}$
SGPT/ALT	3	U/L		$> 5.0 \times \text{ULN} - 20.0 \times \text{ULN}$
	4	U/L		$> 20.0 \times \text{ULN}$
Albumin	3	g/L	< 20	
Glucose	3	mmol/L	$1.7 - < 2.2$	$> 13.9 - 27.8$
	4	mmol/L	< 1.7	> 27.8
Triglycerides	3	mmol/L		$> 5.7 - 11.4$
	4	mmol/L		> 11.4
Creatinine	3	umol/L		$> 3.0 \times \text{ULN} - 6.0 \times \text{ULN} \text{ or}$ $> 3.0 \times \text{Baseline}$
	4	mcmol/L		$> 6.0 \times \text{ULN}$
Potassium	3	mmol/L	$2.5 - < 3.0$	$> 6.0 - 7.0$
	4	mmol/L	< 2.5	> 7.0
Calcium	3	mmol/L	$1.5 - < 1.75$	$> 3.1 - 3.4$
	4	mmol/L	< 1.5	> 3.4
Sodium	3	mmol/L	$120 - < 130$	$155 - < 160$
	4	mmol/L	< 120	> 160
Phosphate	3	mmol/L	$0.3 - < 0.6$	
	4	mmol/L	< 0.3	
CPK	3	U/L		$> 5.0 \times \text{ULN} - 10.0 \times \text{ULN}$
	4	U/L		$> 10.0 \times \text{ULN}$
Total Cholesterol	3	mmol/L		$10.34 < - 12.92$
	4	mmol/L		> 12.92

Note: A post-baseline value must be more extreme than the Baseline value with at least one CTCAE grade of worsening to be considered a potentially clinically important finding.

Table C-3. Criteria for Potentially Clinically Important Vital Sign Values

Vital Sign	Category	Criteria for Potential Clinically Significant Vital Signs
Systolic blood pressure	Low	Value \leq 90 mmHg and decrease \geq 20 mmHg from Baseline
	High	Value \geq 160 mmHg and increase \geq 20 mmHg from Baseline
Diastolic blood pressure	Low	Value \leq 50 mmHg and decrease \geq 10 mmHg from Baseline
	High	Value \geq 100 mmHg and increase \geq 10 mmHg from Baseline
Pulse	Low	Value \leq 50 bpm and decrease \geq 15 bpm from Baseline
	High	Value \geq 120 bpm and increase \geq 15 bpm from Baseline
Weight	High	$>$ 7% increase from Baseline
	Low	$>$ 7% decrease from Baseline

